Pre-Analysis Plan

COVID-19 Health Messaging to Underserved Communities

NCT04371419

This Draft: May 14, 2020

1. Introduction

In the US, recent statistics show that African American and Latinx communities bear a disproportionate burden from Covid-19. Reaching vulnerable and underserved populations is therefore crucial to combating the disease. However, most public messaging campaigns are not targeted toward underserved communities and don't address fears of social stigma, mistrust in the healthcare system, or concerns about immigration status.

This study aims to tackle these issues by delivering video messages, recorded by a racially- and ethnically-diverse set of doctors from Massachusetts General Hospital and the Lynn Community Health center, to a large sample of black and Latinx individuals across the US.

The study has two purposes

1. Identify the combination of videos that are the most effective among those we have, for broad scale up in a second phase.
2. Test some fundamental hypotheses that would apply in a broader sample.

We are cross-randomizing both the message content and the race/ethnicity of the doctor delivering the message. All messages contain information on the symptoms of Covid-19, social distancing, hygiene and mask wearing. Experimental variants include: a) explicit acknowledgment of inequalities pertaining to i) treatment by the healthcare system, ii) impacts to immigration status from seeking care or iii) economic opportunity; b) variation in whether the social distancing and hygiene information is delivered by [name] of the CDC or by the diverse set of doctors; and c) giving debiasing information about the (relative lack of) stigma associated with wearing a mask in public.¹ Subjects see the video messages recorded by a) doctors of concordant race or ethnicity (African-American doctors for African-American subjects or Latinx doctors for Latinx subjects) or b) doctors of discordant race or ethnicity (white, non-hispanic or Asian doctors).

We aim to understand which messaging strategies are most successful at communicating information about Covid-19 to underserved communities. The goal is to understand how to best structure messaging to make them more impactful. We are measuring "impact" as a) trust in information coming from the healthcare system; b) attention and retention of key facts about Covid-19 presented in the videos; c) interest in following the advice in the videos pertaining to social distancing, hygiene and mask-wearing;

¹See Appendix Section A for transcripts of the videos.

and d) health-seeking behavior.

We hypothesize that overall videos delivered by concordant messengers will be more effective. Moreover, acknowledging the “elephant in the room” –i.e., explicit acknowledgment of inequalities – will make the videos more impactful, especially for discordant doctor messengers. We also hypothesize that videos delivered by our partner doctors (even of discordant race or ethnicity) will be more impactful than one delivered by a representative of the CDC. Finally, for individuals who believe that mask wearers are likely to be viewed as sick or up to no good by larger than what we are informing them, we predict that presenting information about beliefs will increase demand for mask wearing.

2. Treatments, and Experimental Protocols

2.1 Treatments

Each subject watches three videos. Each video features a different doctor. All partner doctors viewed in the videos by a given subject are of the same racial or ethnic background.²

1. Video 1:

- Introduction
- Discussion of symptoms
- Acknowledgement of “elephant in the room” issues, where applicable.

2. Video 2:

- Information about social distancing and hygiene

3. Video 3:

- Information about masks

We are varying four aspects of the videos across treatments:

1. Racial or ethnic concordance with partner doctors in the videos (note that we side-step the issue of language: for Spanish speakers, they can chose English or Spanish, and there are non ethnically Hispanic doctors speaking in Spanish).³
2. Video 1 content: Elephant in the room
 - No elephant in the room content
 - Elephant in the room 1: Trust or Fear
 - Elephant in the room 2: Economic Inequality

²However, some individuals may see two black doctors and [name] from the CDC, a white doctor and representative of the US government.

³However we do not have recordings in other languages.

3. Identity of the doctor delivering Video 2

- Pre-recorded video of [name] of the CDC in front of the White House
- Partner doctor

4. Video 3 content: mask debiasing

- Basic mask information, no perceptions information
- Basic mask information, perceptions information
 - For the latinx community, the video discusses perceptions that the mask-wearer is sick.
 - For the black community, the video discusses perceptions that the mask-wearer is “up to no good.”
 - In both cases the message reports responses from a prior survey of perceptions that mask wearers in photos of the same racial/ethnic group are “protecting the community.”

All of the video scripts can be found in Appendix Section A. Figure 1 shows how these different treatments are incorporated in the randomization design.

Figure 1: Treatment Design: There are 8 content-variants for each video, shown here. Cell 1c/d includes the baseline information package. For each combination of message content, the partner doctors in the video may either be of a concordant (c) or discordant (d) racial/ethnic background.

All treatments receive basic information +	Doctor-Delivered CDC Message	[name] -Delivered CDC Message	Elephant 1: Fears (L) or Trust (A)	Elephant 2: Economic Inequality
No Mask Debiasing	1c/d	2c/d	3c/d	4c/d
Mask Debiasing	5c/d	6c/d	7c/d	8c/d

2.2 Recruitment and Sampling

We are using Lucid to recruit a sample and to compensate subjects for their participation. Our total target sample size is 15,000 subjects, 10,000 African American respondents, and 5,000 Hispanic respondents. We require all participants to be age 18 or older. We plan to draw from two samples (within each racial/ethnic group).

1. 5% will be drawn from individuals with a college education or beyond
2. 95% will be drawn from individuals with a high school education or below

2.3 Experimental Protocols and Treatments

Our experiment has the following structure:

1. Recruitment and Baseline survey
 - (a) Recruit target sample via Lucid
 - (b) For Hispanic respondents, elicit a preference for English or Spanish. Those with a preference for Spanish will be given Spanish language survey questions and will see treatment videos recorded in Spanish as well.⁴
 - (c) Collect demographic information and healthcare experience. Several demographics variables are being collected directly by Lucid.
2. Randomize Subjects to treatment
 - Treatment scripts are tailored to each racial/ethnic group
 - Within racial/ethnic group, treatment is stratified on age, gender and geographic region.
 - Randomization is at the individual level according to Figure 1.
 - There will also be a control group who will receive COVID-19 information at the very end of the survey.
3. Video delivery for all individuals not in the pure control group.
 - (a) After each of the three videos, respondents evaluate the video's usefulness, and trustworthiness, along with the respondents intention to follow the advice in the video and share information from the video.
 - (b) Prior to the third video (masks), individuals will answer questions about second order beliefs about mask wearers.
4. Endline survey
5. Videos shown to the pure control group.
6. Debrief script
7. Follow-up survey
 - (a) We are tentatively planning to follow up with participants several days post-treatment
 - (b) The chief purpose would be to measure health-seeking and health-preserving behaviors.⁵
8. Once we learn which messaging strategy is most effective, we will scale up that treatment more broadly (distributing it through social media etc.)

⁴The one exception is the CDC video with [name]. This is always shown in English.

⁵We do not commit on analyzing this data or even fully implementing a follow up because it is quite difficult to successfully follow up with online survey participants, so it will depend on our success in finding people in our pilot.

3. General Hypotheses to be Tested

This section lists the general hypotheses we want to test. For those, we are planning to run broadly pooled treatments (and specific interactions specified below).

Main hypotheses:

1. What is the overall effect of any combination of videos, compared to the control group?
2. Does racial concordance between the doctor messenger and recipient give the message higher impact across the board?
3. Does addressing the “elephant in the room” lead to greater video impact?
4. Are the doctors in our videos more effective at communicating the same message with underserved populations than [name], a representative of the CDC and the US federal government’s response? (To test this hypothesis, we will focus on the outcomes associated with the social distancing and hygiene video.)
5. Does the [name] video lead to a "shut down" and refusal to pay attention to the rest of the message: for this we can compare the attitude to masks (which are not mentioned in the [name] video, and are discussed in a video segment shown after that with [name]).
6. Does providing information on perceptions about mask wearers change an individual’s willingness to wear a mask? We proxy for willingness to wear a mask in two key ways: a) demand for information about mask-making, b) incentivized allocations of money to support masks for black or latinx communities vs. other charitable projects targeted at the same communities.
 - (a) Focus groups and baseline data suggest that on average, members of the black community worry that they will be viewed as “up to no good” when wearing a mask by a larger percent of Americans than actually hold that belief. For Latinx communities, the fear is more that mask-wearers will be perceived to be sick, generating a different kind of stigma.
 - (b) Specifically, we predict that the effects of the “social norm debiasing” treatment should vary with the respondent’s priors about how mask-wearers are viewed. Individuals learning that their beliefs were too pessimistic should increase their willingness to wear a mask, while those learning that their beliefs were too optimistic (this should be rare) might respond the opposite way.

Secondary hypotheses involving specific interactions between treatments:

1. Racial concordance might also give more credibility to other information presented in the videos such as info delivered by [name] of the CDC or information about mask perceptions.
2. Does addressing the “elephant in the room” increase impact of the videos more for discordant doctor messengers?
3. Does acknowledging the “elephant in the room” give greater credibility to other information in the video, such as the CDC video or the mask debiasing information? (Interaction effects with CDC treatment and with mask debiasing treatment.)

In addition to testing these hypotheses, we will also explore what is the most effective combination of messages and messengers overall (after “smart statistical pooling” of variants that prove similar), and what is its effect, accounting for any small sample bias induced by picking a winner.

4. Data Collection and Outcomes

We will run our experiment beginning on May 13, 2020. The data will be collected from respondent surveys. There is a short baseline module before the treatment group views the videos. Before the mask video (video 3), we elicit beliefs about perceptions of mask wearers. Then following video 3, there is an endline outcome module that all participants complete. (The control group only sees the videos after the endline has been completed.) We may decide at a later date to do a follow up survey with a subsample of the original participants. (Clearly, for this exercise, there will no longer be a valid control group. All comparisons will be done across treatments.) All of the survey responses will be downloaded is a .csv file for cleaning and analysis in STATA.

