5.3 Regression Analysis

We will do two types of analysis: identifying effective videos in our sample, and general tests of the hypotheses described above.

- Best treatment

We are interested in selecting the best combination of types of video for scale up. In order to identify the most effective combination of videos, we will adapt a disciplined pooling methods of Banerjee et al (2020) for selecting the most effective combination of treatments (to a settings were we have large

sample within each of 16 treatment cells), and Andrews et al (2020) to correct for small sample bias in estimating the impact the most effective method.⁶

For this specific question of whether *our* messages of a given type (concordant race, correcting priors, etc), since random assignment is done by individuals, we do not adjust standard errors. This is the correct analysis for scaling up these videos per-se.

- Hypothesis tests

In order to test the hypotheses listed above, we run the following contrasts (Hispanic and Black will be run separately for all the contrasts:

Main hypotheses tests:

1. Is there any impact of the videos (treatment vs control)
2. Concordant vs. discordant messengers: pooled across all
3. [name] with "no elephant" and the two different versions of "elephant in the room", no [name] each compared to the "no elephant, no [name]" condition
4. [name] versus everything else.
 - For social distancing and hygiene (largest effect expected here for the [name] treatment)
 - For other outcomes
5. Mask-debiasing treatment on mask outcomes, heterogenous based on respondent prior beliefs (lower or higher than 8 out of 10 people think mask wearer is helping the community).

Secondary hypotheses tests

1. [name] treatment effects will be interacted with concordant doctor
2. [name] treatment effect will be interacted with social debiasing treatment (which may be less effective after presenting [name])
3. Elephant treatment will be interacted with concordant doctor
4. Mask treatment effect will be interacted with concordant doctor
5. Mask treatment effect will be interacted with elephant treatment
6. [name] treatment effect will be interacted with elephant treatment
7. Gender of provider will be interacted with concordant doctor and/or respondent gender

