5.4 Heterogeneous Effects

We are interested in understanding differences by baseline characteristics. We believe that there may be heterogeneous treatment effects based many dimensions. The three most important heterogeneous treatment effects are the following:

1. Heterogeneity in the effectiveness of the mask treatment by prior beliefs (i.e. whether people would update up or down from their priors based on the message seen).
2. Heterogeneity by gender, especially for understanding impacts on masks. (Our background research suggests that African American men feel mask stigma most strongly.)
3. Heterogeneity by language choice within the Latinx group (in particular for CDC message which is not translated)

We are also interested in exploring heterogeneity on the following categories of traits/characteristics.

- Vulnerability to Covid-19 (age, essential worker status, pre-existing health conditions)
- Level of baseline knowledge (education, prior interaction with the health-care system, information sources)
- Location effects (covid-19 policies, covid-19 infection rates, and socio-economic conditions)

Given the many ways to cut the data we will follow the methodology of Chernozhukov et al (2018) for this latter set of potential heterogeneous treatment effects.⁷

6. Robustness

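### For Spanish-choosing Hispanic respondents the CDC arm changes language as well as messenger, so the pooled Hispanic CDC contrasts cannot by themselves be read as a messenger effect

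*Combined protocol and SAP*

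**What the plan says.** Section 2.3, step 1(b), has Hispanic respondents choose a language before randomisation: "For Hispanic respondents, elicit a preference for English or Spanish". It continues: "Those with a preference for Spanish will be given Spanish language survey questions and will see treatment videos recorded in Spanish as well". Footnote 4 makes one exception, the clip featuring the CDC representative: "This is always shown in English".

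Main hypothesis 4 in Section 3 holds content fixed and asks about the messenger: "Are the doctors in our videos more effective at communicating the same message with underserved populations" than the CDC representative. Hypothesis 5 asks whether that clip makes viewers stop attending to what follows, judged on mask attitudes.

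Section 5.3 tests these in two places. Main test 3 has a limb comparing the CDC clip with the condition that has neither that clip nor elephant content. Main test 4 compares the CDC clip with all other arms. The level of analysis is stated as "Hispanic and Black will be run separately for all the contrasts", with no language split in the list of main tests. Language choice enters as a control variable. Section 5.4 places language choice among its three leading heterogeneity analyses, "in particular for CDC message which is not translated".

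**The concern.** A Spanish-chooser is randomised between a partner doctor speaking Spanish and the CDC representative speaking English. Two things change at once, and the hypothesis is about only one of them. The design does protect the concordance contrast, because Section 2.1 provides non-Hispanic doctors who speak Spanish. No such provision exists for the CDC clip.

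If hearing the clip in English lowers comprehension, the distortion runs in the direction the plan predicts, since Section 1 expects partner doctors to outperform the CDC representative. It would act most directly on retention of the social distancing and hygiene content, the outcomes on which Section 3 focuses hypothesis 4. A Hispanic finding that doctors communicate better could then come partly or wholly from an untranslated clip.

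**Working it through.** The documents give no alpha, power, SD or expected effect, so there is no stated figure to reproduce.

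**Inputs from the documents.** 5,000 Hispanic respondents (Section 2.2). 8 content variants × 2 (concordant or discordant) = 16 treatment cells, of which the CDC clip occupies four: 2c, 2d, 6c and 6d (Figure 1). A control group of unstated size.

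**Assumptions.** Control group the size of one cell, equal allocation, SD = 1, two-sided 5%, 80% power, no exclusions. The comparator in test 4 is read as the other treated arms. The share choosing Spanish (s) and the language loss among them (λ, in SD) are not given, so ranges are used.

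**Group sizes.** 5,000/17 = 294.1 per cell. CDC clip: 4 × 294.1 = 1,176. Test 3 comparator (1c/d and 5c/d): 1,176. Test 4 comparator: 12 × 294.1 = 3,529.

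**Standard errors.** Test 3 limb: √(2/1,176) = 0.0412. Test 4: √(1/1,176 + 1/3,529) = 0.0337.

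**Shift.** Language choice precedes randomisation, so the share s is the same in expectation in every arm. The pooled difference is therefore the messenger effect plus s × λ.

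**False-positive rate with no messenger effect.** P(|Z + sλ/SE| > 1.96):

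| s | λ (SD) | shift (SD) | test 3 limb | test 4 |
|---|---|---|---|---|
| 5% | 0.1 | 0.005 | 5.2% | 5.3% |
| 10% | 0.2 | 0.02 | 7.7% | 9.1% |
| 20% | 0.2 | 0.04 | 16% | 22% |
| 20% | 0.4 | 0.08 | 49% | 66% |
| 30% | 0.4 | 0.12 | 83% | 95% |

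With a 20% control share (1,000 versus 1,000, or versus 3,000), the 20%/0.4 row becomes 43% and 59%.

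**Does the planned language control remove the shift?** In 1,000 simulated data sets of 4,706 respondents, with a quarter assigned the clip, s = 0.3, λ = 0.3 and no messenger effect, the clip coefficient adjusted for language averaged −0.088, against an expected −0.3 × 0.3 = −0.09. Adding a clip × language term gave 0.001 for English-choosers. The main-effect control leaves the shift in place, and the interaction model removes it.

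**Can the interaction test detect the problem?** The pooled detectable difference for test 4 is (1.960 + 0.842) × 0.0337 = 0.094 SD. For the interaction it is 0.0943/√(s(1 − s)): 0.31 SD at s = 10% and 0.24 SD at s = 20%. At s = 20%, a loss of 0.2 SD is below that threshold, yet it raises the test 4 false-positive rate to 22%.

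**The case against.** The strongest reply is that the plan has seen the problem. Section 5.4 says the clip is untranslated, ranks the language split among its three leading heterogeneity analyses, and keeps it apart from the exploratory set sent to machine learning. Because language is chosen before randomisation, that split yields a clean English-chooser comparison. This stands. What is missing is a statement of which estimate answers hypothesis 4 and how the pooled Hispanic result is to be read.

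A reader might infer that the Hispanic contrasts cannot answer the question at all. The documents do not support that. The step 1(b) item records a preference, not an inability to follow English, and with a small share or loss the distortion is close to nil.

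A reader might also carry the problem in full to hypothesis 5. The mask segment that follows is in Spanish for Spanish-choosers, so lost comprehension of Video 2 does not act on it directly. The hypothesis is affected only if the untranslated clip itself causes disengagement.

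Nor do secondary tests 1 and 2, which interact the CDC clip with concordance and with mask debiasing, clearly inherit the bias. A language loss that is additive across those factors cancels in the interaction.

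Finally, restricting to English-choosers narrows the population, although the hypothesis concerns underserved groups broadly. This is a real cost and a reason to keep the pooled estimate alongside.

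**Conclusion.** The concern holds as a matter of interpretation. Followed as written, the pooled Hispanic estimates in the CDC limb of test 3 and in test 4 mix messenger with language, and the planned language control does not separate them. If English delivery reduces comprehension, the mixing favours the plan's prediction.

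The size cannot be fixed from the documents. It ranges from negligible to large enough to produce a false messenger finding about half the time or more, depending on the Spanish-choosing share and the language loss. All the rates rest on the assumed allocation, SD and alpha.

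The randomisation is sound, the Black-sample contrasts are untouched, and the pooled Hispanic estimate remains valid for choosing which videos to scale up.

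**What to change.** In Section 5.3, add for Hispanic respondents:

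- The messenger conclusion for hypothesis 4, and the messenger reading of hypothesis 5, rest on the CDC-clip effect among English-choosers, taken from a clip × language model or from that subgroup.
- Spanish-choosers are reported separately, labelled as English CDC clip versus Spanish-language doctor, with no messenger conclusion drawn from them.
- The pooled estimate is kept and labelled as the effect of the videos as delivered, for the scale-up aim.
- A non-significant clip × language interaction is not grounds for reading the pooled estimate as a messenger effect.

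Secondary tests 1 and 2 need no change. No new data are needed, and the comparison stays randomised.

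The cost is precision and scope. For test 4 the detectable difference rises from 0.094 SD to 0.0943/√0.8 = 0.105 SD at a 20% Spanish share, and to 0.133 SD at 50%. For the test 3 limb it rises from 0.116 to 0.129 SD at 20%. The Hispanic messenger claim is then limited to English-choosing respondents.

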4.1 Baseline Survey Variables

The baseline survey includes demographic characteristics, information about health status, and access to healthcare:

- Education
- Household Size
- Employment Status
- Essential Worker Status
- Insurance Status
- Pre-Existing Health Conditions
- Healthcare Usage Patterns
- Health Information Sources
- Food Security

See Section 5, below for a summary of our key Endline survey variables.

